## 15. DATA AND SAFETY MONITORING PLAN

*A specific data and safety monitoring plan is only required for greater than minimal risk research. For guidance on creating this plan, please see the [Guidance Document](#) on the HRPP website.*

*Part I – this part should be completed for all studies that require a DSMP.*

*Part II – This part should be completed when your study needs a Data and Safety Monitoring Board or Committee (DSMB/C) as part of your Data and Safety Monitoring Plan.*

### Part I: Elements of the Data and Safety Monitoring Plan

- *Indicate who will perform the data and safety monitoring for this study.*
- *Justify your choice of monitor, in terms of assessed risk to the research subject's health and well being. In studies where the monitor is independent of the study staff, indicate the individual's credentials, relationship to the PI, and rationale for selection*
- *List the specific items that will be monitored for safety (e.g. adverse events, protocol compliance, etc)*
- *Indicate the frequency at which accumulated safety and data information (items listed in # above) will be reviewed by the monitor (s) or the DSMB/C.*
- *Where applicable, describe rules which will guide interruption or alteration of the study design.*
- *Where applicable, indicate dose selection procedures that will be used to minimize toxicity.*
- *Should a temporary or permanent suspension of your study occur, in addition to the IRB, indicate to whom will you report the occurrence.*

### Part II: Data and Safety Monitoring Board or Committee

- *When appropriate, attach a description of the DSMB.*
- *Provide the number of members and area of professional expertise.*
- *Provide confirmation that the members of the board are all independent of the study.*

[name], will be responsible for ensuring participants' safety on a daily basis. As the proposed project is a Stage 2 study of the effectiveness of MBIs to achieve improved sleep quality, and these MBIs have been implemented with health care workers in other personalized trials, the level of risk appears to be that of those experienced in everyday life. [name], the study coordinator, and [name] will regularly monitor participant safety evaluate the progress of the study, review procedures for maintaining the confidentiality of data, review the quality of data collection, management, and analyses at weekly team meetings.

To assure data accuracy, the Data Manager will process monthly reports to search for errors and generate basic reports for dissemination at regular meetings. Protocol compliance will be reviewed during regular meetings between [name], [name] and the research team. Finally, [name] will perform a random audit of 5% of enrollments, and provide continual feedback to improve the quality of informed consent and data collection.

[name] and [name] will convene no less than monthly to comprehensively review participation in the study. As this is a minimal risk study, no safety officer has been appointed for this study. The study team will regularly convene to share safety reports with [name]. All collected data will be stored in the RedCAP program, a Northwell IRB and Research IT security approved location, housed on the Northwell IT approved server. All data will be de-identified before analysis and before being made available for data sharing. Following the onset of data collection, the Data Manager will provide this group with biweekly reports of the aggregate data, progress of the study, including participant accrual, protocol compliance, and problems encountered.

## 16. WITHDRAWAL OF SUBJECTS

- *Describe anticipated circumstances under which subjects will be withdrawn from the research without their consent*
- *Describe procedures for orderly termination*
- *Describe procedures that will be followed when subjects withdraw from the research, including partial withdrawal from procedures with continued data collection.*

Circumstances under which participants will be withdrawn from the research without their consent include not meeting objective verification of short sleep duration (<7 hrs per 24hr periods during 2 week run-in as measured by a Fitbit activity tracker), failure to maintain protocol adherence, and self-reported adverse side effects to interventions. A potential participant will not be randomized to receive the intervention protocol until he/she has demonstrated at least 80% adherence to continuous Fitbit monitoring (activity recorded > 12 hours/day, and

recorded sleep activity >180 minutes) and response to survey questionnaires during the baseline period.

Potential participants will be notified of the possibility of being removed from the study before intervention randomization due to adherence issues in the informed consent. Participants who fail to maintain minimum adherence during baseline will be notified by the research team in the first 10-14 days of baseline participation. These participants will stop receiving notifications and survey prompts and will receive instructions to un-link their Fitbit device.

Participants who fail to maintain protocol during the intervention period will be contacted by a member of the study team with a reminder of the study protocol and will be informed that this may impact their continued study eligibility. If it is determined that the participant will be withdrawn from the study, the participant will be notified of their withdrawal from the study by the research team. The participant will stop receiving notifications and survey prompts and will be sent instructions to un-link their Fitbit device. The participant will be able to keep their Fitbit device.

Should a participant choose to withdraw from research, they will be instructed to send a letter or e-mail to the attention of the Principal Investigator at our [name] office, or to email [[contact]](mailto:[contact]), an e-mail account monitored by IRB-approved members of the research team. Participants will be contacted by a member of the research team confirming their study withdrawal, and to answer any questions the participant may have. The participant will stop receiving notification and survey prompts and will be sent instructions to un-link their Fitbit device. They will be able to keep their Fitbit device. Data collection will stop the business day the letter or e-mail is received. All data up until the receipt date of the letter or e-mail will be included in the research study.

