### **Sample size justification:**

The primary aim of this study is to evaluate the effect of a personalized MBI on increasing the average daily sleep duration in working at Northwell Health. A sample size of 30 participants per arm achieve 80% power to detect a minimum effect size of 0.7 expected by one of the three Aim 2 interventions. Calculations were based on GEE tests for repeated measures considering a total of 28 daily measurements (4 weeks) per intervention, at a significance level of 0.05. The within subject standard deviation  $\sigma$  is anticipated to be maximum 2h, with an auto-regressive AR(1) base correlation of 0.95 taken at two successive timepoints. Estimated effect size and correlation values were derived from a previous fatigue study that employed similar intervention/design and collected sleep duration as exploratory endpoint.

The **randomization schedule** will be set up by a member of the Institute of Health System Science data team and provided to the data analyst assigned to this trial.. Randomization will occur with a fixed seed value for the purposes of repeatability and auditability, and the list of participants will be split into two groups using a

random shuffle function that takes that seed as input. The order in which an individual becomes eligible for one of these randomizations will determine the placement given (i.e. the first person eligible will be randomized to the intervention order given to participant 1 and continue sequentially). Eligibility is obtained by a participant maintaining at least 80% adherence of survey response, Fitbit wear  $\geq 12$  hours a day 80% of days, and 80% sleep data  $\geq 180$  minutes available through the baseline run-in period. The data analyst will alert the research coordinator of the assigned randomization once a participant becomes eligible during the baseline run-in period. As this pilot is not blinded to study coordinators, this concealed allocation involving the data analyst alerting the study coordinator of intervention assignment will be used to prevent bias by blinding the sequence up until time of randomization.

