### **Analytical Plan**

**Primary Outcome** – Mean Within-Subject Difference in daily sleep duration during 3 treatment periods from baseline. Participant's sleep duration will be measured objectively using Fitbit devices and by self-reported questionnaires. The Fitbit devices will collect information continuously that will be stored in Fitabase, a secure, online portal. Participant sleep activity will be aggregated by day.

Analysis of Primary Outcome: The effect of the personalized MBI intervention on individual's sleep duration will be assessed in each arm separately. Individual changes in the average daily sleep durations between the run-in and each treatment period will be reported using mean (95% confidence intervals CIs). Bland-Altman plots will be constructed to visualize the agreement between the Fitbit reported and self-reported sleep duration. The effects of treatment on sleep duration will be assessed using generalized estimating equations (GEE) with an unstructured variance-covariance matrix for measures on the same day to that night's sleep. This model accounts for possible autocorrelation and linear trends between sleep duration across time. The GEE models will include time of day of treatment exposure (AM versus PM) as a covariate.

**Exploratory Aim 1 Outcomes** - Mean Within-Subject Difference in daily sleep quality and other physiological factors during 3 treatment periods from baseline. This aim will explore the effects of the personalized intervention on sleep quality components (sleep onset, sleep staging, and overall sleep score) and physiological factors (breathing/resting heart rate, heart rate variability (HRV) and physical activity). All these measurements will be recorded and aggregated daily by the Fitbit device.

Analysis of Exploratory Aim 1 Outcome: The effect of the personalized MBI intervention on individual's sleep quality and physiological factors will be assessed in each arm separately. Individual changes in the average daily sleep quality (e.g., score), heart rate and daily average number of steps between the run-in and each treatment period will be reported using means (95% CIs. GEE models will be employed to test the effect of the intervention of sleep quality and physiological factors.

**Exploratory Aim 2 Outcomes** – Mean Within-Subject Difference in perceived stress, anxiety and depression scores measured objectively during 3 treatment

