## **17. RISKS TO SUBJECTS**

- *Describe any potential risks and discomforts to the subject (physical, psychological, social, legal, or other) and assess their likelihood and seriousness and whether side effects are reversible. Where appropriate, describe alternative treatments and procedures that might be advantageous to the subjects.*
- *Include risks to others , like sexual partners (if appropriate)*
- *Discuss why the risks to subjects are reasonable in relation to the anticipated benefits and in relation to the importance of the knowledge that may reasonably be expected to results*
- *Describe the procedures for protecting against or minimizing any potential risks, including risks to confidentiality, and assess their likely effectiveness.*

This study poses no greater than minimal risk to participants. Monitoring for adverse side-effects will be performed during the N-of-1 trial. Participants will be encouraged to adhere to the protocol but will also be told that they can discontinue intervention at any time.

It is not uncommon for participants to experience temporary soreness and/or fatigue following low-intensity physical activity (walking) or stretching (yoga). There is always a risk that physical activity can result in musculoskeletal injury. Mindfulness meditation may include experiences that are pleasant, unpleasant, or neutral. It can lead to states of ease, joy, relaxation, peace and a sense of wellbeing. Unpleasant experiences such as agitation, physical discomfort, sleepiness, sadness and anger are also common. Such experiences are usually temporary.

If participants experience discomfort during their intervention sessions, they will be instructed to immediately stop the activity and contact a research coordinator.

There is always a risk of potential emotional distress in answering survey questions examining one's stress levels.

There is also the potential risk of loss of privacy of information pertaining to research material collected by the study. Yet, we will take precautions, described below, to minimize these risks.

We will emphasize to subjects in the intervention arm that they can withdraw from the N-of-1 trial completely at any point, particularly if they experience any concerning side-effects. Participants will be instructed to contact 911 or go to the nearest emergency room in the event of a medical emergency. Adverse events will be reported to the PI, IRB and sponsor as outlined in the DSMP.

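### Withdrawal for side effects or non-adherence ends sleep measurement with no follow-up and no missing-data plan, so the primary contrast is open to modest bias of unknown direction

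*Combined protocol and SAP*

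**What the plan says.** Section 16 lists the grounds for withdrawing someone from the research without consent. Besides failing the run-in sleep check, they are "failure to maintain protocol adherence, and self-reported adverse side effects to interventions". For a participant withdrawn after failing to keep to the protocol during the intervention, it continues: "The participant will stop receiving notifications and survey prompts and will be sent instructions to un-link their Fitbit device". That decision follows a reminder and is discretionary, and no threshold is given. For voluntary withdrawal, section 16 says that collection ends on the business day the notice arrives and that earlier data are kept. The form's own prompt in section 16 asks about partial withdrawal with continued data collection. The answer describes no such route.

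Section 17 tells participants that they may discontinue the intervention at any time and, separately, that they may withdraw from the trial completely.

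Section 12 (Analytical Plan) compares run-in with the treatment periods within each arm, with the effect "assessed using generalized estimating equations (GEE) with an unstructured variance-covariance matrix". It names no missing-data assumption, analysis set or sensitivity analysis. The nearest text is the target in sections 8, 9 and 11 of 60 participants with any data after randomization.

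**The concern.** Sleep duration is recorded by a device the participant already wears, so it could still be measured after the sessions stop. The plan does not use this. Someone removed for side effects or non-adherence keeps a full run-in but has a truncated set of treatment nights. If the reason for leaving relates to how sleep was changing, the remaining treatment nights come from a selected group.

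An unweighted GEE is guaranteed valid in general only when data are missing completely at random. For a continuous outcome it is also nearly unbiased when dropout depends on observed data, provided the mean and working covariance are correctly specified. Section 12 relies on an unstructured matrix for this, and such a matrix cannot be estimated from nightly data with about 30 people per arm. At stake is the primary result, the change in sleep duration from run-in.

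**Working it through.** **1. The planned effect, for scale.** Section 12 states: "A sample size of 30 participants per arm achieve 80% power to detect a minimum effect size of 0.7", "considering a total of 28 daily measurements (4 weeks) per intervention", "at a significance level of 0.05". The SD "is anticipated to be maximum 2h, with an auto-regressive AR(1) base correlation of 0.95 taken at two successive timepoints". The unit of 0.7 is not given. For the mean of m = 28 nights under AR(1) 0.95, the variance factor is f = (sum of the correlation matrix)/m² = 0.654. The two-group size is n = 2(1.96 + 0.842)² f SD²/δ².
- 0.7 in SD units: 2 × 7.849 × 0.654/0.49 = 20.95, so 21 per arm; power at 30 per arm is 91.8%.
- 0.7 h with SD 2 h: 2 × 7.849 × 0.654 × 4/0.49 = 83.8, so 84 per arm; power at 30 per arm is 38.8%.

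Neither reading returns 30 per arm at 80% power, so both are carried: 0.7 h = 42 min, or 0.7 × 2 h = 1.4 h = 84 min.

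**2. Attrition in the documents.** No dropout rate is given. Section 8 allows up to 65 randomized to reach 60, and 5/65 = 7.7%. This is a replacement allowance rather than a dropout rate, so 20% and 30% are added as assumptions.

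**3. A simple formula.** If withdrawn people gave no treatment nights, bias = withdrawn fraction × (mean change in those retained − mean change in those withdrawn). At 7.7%, assumed differences of 30, 60 and 120 min give 2.3, 4.6 and 9.2 min. The sign is the sign of the difference, and the documents give no data on it.

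**4. Simulation.** 200,000 participants; run-in plus six two-week means; SD 2 h and AR(1) 0.95 from section 12; true effect 0.7 h. Assumptions not in the documents: between-person SD of response 0.5 h; dropout only after the first treatment period; dropout log-odds of 1.0 per 1.5 h of observed change (missing at random) or per SD of true response (missing not at random). Bias of a GEE with independence working correlation, in minutes:

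| Dropout | Poor responders leave | Good responders leave |
|---|---|---|
| 7.7% | +1.2 to +1.6 | −1.6 to −1.7 |
| 20% | +2.6 to +4.1 | −2.6 to −3.5 |
| 30% | +4.5 to +5.5 | −4.2 to −6.2 |

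With the correct covariance, bias stays within about 0.5 min under missing at random and about 1.1 min under missing not at random (Monte Carlo error about 0.3 min). A smaller run (60 participants, zero true effect, response SD 0.7 h, poor responders leaving) gave +0.05 to +0.09 h, or 3 to 5 min, at 14% to 21% withdrawn.

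Against 42 min, the range is 1.2/42 = 3% to 6.2/42 = 15%. Against 84 min, it is 1% to 7%.

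**5. Can the planned covariance be fitted?** Run-in plus treatment is 14 + 84 = 98 nights. An unstructured correlation matrix has 98 × 97/2 = 4,753 parameters; even 28 nights need 28 × 27/2 = 378. Each arm has about 30 people and is analysed separately. A simpler structure will be needed, and the Analytical Plan names none, although the sample-size paragraph assumes AR(1).

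**The case against.** A reader might infer that the effect is biased upward because poor responders are removed. The documents do not support that. No section links withdrawal to sleep response, and the sign in the simulation follows from who is assumed to leave. Upward bias is plausible if dislike or side effects drive exit, or if the run-in adherence rule in section 11 (more than 180 minutes of recorded sleep) is reused during treatment, since very short nights would then count as non-adherence. Section 16 does not say that it is.

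A reader might also infer that GEE is valid only under completely random dropout. That is too strong, as the correct-covariance result shows. The comparison in the working is between working covariances, not between GEE and mixed models as such. The case for changing the model rests on the unstructured matrix being unfittable.

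Other objections stand in part.
- Where adherence is defined (sections 11, 12 and 16), it means Fitbit wear, recorded sleep and surveys, not session attendance. Keeping the device linked recovers little from someone withdrawn for not wearing it, and charging and syncing still take effort.
- The remark in section 17, "Unpleasant experiences such as agitation, physical discomfort, sleepiness, sadness and anger are also common", concerns mindfulness, and the section calls such experiences usually temporary. It does not show that withdrawal will be frequent.
- Un-linking after a side-effect withdrawal is inferred; the quoted instruction sits in the paragraph on failing the protocol.
- The reminder, the option to pause, the run-in adherence screen and the weekly lottery should all limit loss.
- The mean of per-person changes, also to be reported, showed almost no bias under response-related dropout in the main simulation. It was biased by −1.6 to −5.7 min when short baseline sleepers left, so it is not a general safeguard.
- The bias is small beside sampling error. With SD 2 h, AR(1) 0.95 and 30 people, the variance of one person's run-in versus treatment contrast is 3.32 h², so the SE is √(3.32/30) = 0.33 h, about 20 min.

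**Conclusion.** The concern holds in limited form. Followed as written, the plan loses primary-outcome nights for reasons that may relate to response. It has no follow-up after withdrawal, no route for someone who stops sessions but stays, and no missing-data assumption or sensitivity analysis. The consequence is possible bias of unknown direction, roughly 1 to 6 minutes at 8% to 30% dropout if an independence-type GEE is what is finally fitted. That is at most about 15% of the planned effect on the smaller reading and less than a third of one standard error. The dropout rates, response SD and dropout mechanisms are assumptions. This is a cheap improvement to a pilot, not a flaw that undermines it.

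**What to change.** **Section 16.** Separate stopping the sessions from leaving the study. Unless the participant withdraws consent to data collection, keep the Fitbit linked and the sleep diary running to week 16, and record the date and reason for stopping sessions. State what adherence means after randomization. Sections 16 and 17 must be reconciled on what happens to data collection when someone stops the intervention. Who stops sessions need not change.

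**Section 12.** State that all available nights are analysed under the assigned sequence. Replace the unstructured matrix with a parsimonious covariance such as AR(1) in a likelihood-based mixed model, or use weighted GEE, and state the missing-at-random assumption. Add a delta-adjusted sensitivity analysis that shifts the unobserved changes by, say, 0.5, 1 and 2 h in each direction. Say how the AM/PM session-time covariate is coded on nights without a session; otherwise the retained nights could be dropped from the model.

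**Cost.** Protocol and consent wording and a change of model specification. The devices and the Fitabase feed already exist. The downside is a few more participants to keep syncing, with little gain from those withdrawn for not wearing the device.

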## **17. RISKS TO SUBJECTS**

- *Describe any potential risks and discomforts to the subject (physical, psychological, social, legal, or other) and assess their likelihood and seriousness and whether side effects are reversible. Where appropriate, describe alternative treatments and procedures that might be advantageous to the subjects.*
- *Include risks to others , like sexual partners (if appropriate)*
- *Discuss why the risks to subjects are reasonable in relation to the anticipated benefits and in relation to the importance of the knowledge that may reasonably be expected to results*
- *Describe the procedures for protecting against or minimizing any potential risks, including risks to confidentiality, and assess their likely effectiveness.*

This study poses no greater than minimal risk to participants. Monitoring for adverse side-effects will be performed during the N-of-1 trial. Participants will be encouraged to adhere to the protocol but will also be told that they can discontinue intervention at any time.

It is not uncommon for participants to experience temporary soreness and/or fatigue following low-intensity physical activity (walking) or stretching (yoga). There is always a risk that physical activity can result in musculoskeletal injury. Mindfulness meditation may include experiences that are pleasant, unpleasant, or neutral. It can lead to states of ease, joy, relaxation, peace and a sense of wellbeing. Unpleasant experiences such as agitation, physical discomfort, sleepiness, sadness and anger are also common. Such experiences are usually temporary.

If participants experience discomfort during their intervention sessions, they will be instructed to immediately stop the activity and contact a research coordinator.

There is always a risk of potential emotional distress in answering survey questions examining one's stress levels.

There is also the potential risk of loss of privacy of information pertaining to research material collected by the study. Yet, we will take precautions, described below, to minimize these risks.

We will emphasize to subjects in the intervention arm that they can withdraw from the N-of-1 trial completely at any point, particularly if they experience any concerning side-effects. Participants will be instructed to contact 911 or go to the nearest emergency room in the event of a medical emergency. Adverse events will be reported to the PI, IRB and sponsor as outlined in the DSMP.

